#### 6.4.6 Exit / Discontinuation Criteria

Participation of a subject in this clinical study may be discontinued for any of the following reasons:

- Screen failure
- AE/serious adverse event (SAE)
- Death
- Lack of efficacy
- Lost to follow-up
- Physician decision
- Protocol violation
- Study terminated by Sponsor or regulatory authority
- Technical problems with the study device
- Withdrawal by subject

If a subject withdraws prematurely from the study due to the above criteria or any other reason, study staff should make every effort to complete the full panel of assessments scheduled for the Early Exit Visit. The reason for subject withdrawal must be documented in the eCRF.

In the case of subject lost to follow-up, attempts to contact the subject must be made and documented in the subject's medical records. Withdrawn subjects will not be replaced.

A subject will be considered lost to follow-up if he or she fails to return for scheduled visits and is unable to be contacted by the study site staff. The following actions must be taken if a subject fails to return to the clinic for a required study visit:

- The site will attempt to contact the subject and reschedule the missed visit as soon as possible and counsel the subject on the importance of maintaining the assigned visit schedule and ascertain if the participant wishes to and/or should continue in the study.
- Before a participant is deemed lost to follow-up, the Investigator or designee will make
  every effort to regain contact with the subject (where possible, 3 telephone calls and, if
  necessary, a certified letter to the subject's last known mailing address or local equivalent
  methods). These contact attempts should be documented in the subject's medical record or
  study file.
- Should the subject continue to be unreachable, he or she will be considered to have withdrawn from the study with a primary reason of lost to follow-up.

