# 7.4 Follow-Up Procedures and Therapy Transitions

In this study, there are no specific follow-up procedures or therapy transitions required. Following study completion, subjects will return to their previous care provider.

Alcon products associated with device deficiencies and/or product-related AEs should be returned when possible. Product returns must include the complaint number, which will be provided by study Sponsor after the case is entered in the study Sponsor's Global Product Complaint Management System (GPCMS).

Return any recoverable Alcon Product associated with a product-related AE (adverse device effect [ADE], serious adverse device effect [SADE]) or device deficiency to the Sponsor. Include the SAE/ADE or device deficiency eCRF in the return package. Maintain a copy of shipment tracking information and all documents submitted with the product.

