#### 9.2 Monitoring for Adverse Events

At each visit, after the subject has had the opportunity to spontaneously mention any problems, the Investigator should inquire about AEs by asking the standard questions shown below and report as applicable:

- "Have you had any health problems since your last study visit?"
- "Have there been any changes in the medicines you take because of a new health issue or worsening of an existing health issue since your last study visit?"

In addition, changes in any protocol-specific parameters and/or questionnaires evaluated during the study are to be reviewed by the Investigator. Any untoward (unfavorable and unintended) change in a protocol-specific parameter or questionnaire response that is clinically relevant, in the opinion of the Investigator, is to be reported as an AE. These clinically relevant changes will be reported regardless of causality.

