# 9.5 Follow-up of Subjects with Adverse Events

The Investigator is responsible for adequate and safe medical care of subjects during the study and for ensuring that appropriate medical care and relevant follow-up procedures are maintained after the study.

The Investigator should provide the study Sponsor with any new safety information (which includes new AEs and changes to previously reported AEs) that may affect the safety evaluation of the study treatment. For AEs that are unresolved/ongoing at time of subject exit from study, any additional information received at follow-up should be documented in the eCRFs up to study completion (i.e., database lock).

All complaints received after this time period will be considered and processed as spontaneous (following the post-market vigilance procedures) and should be communicated to the study treatment's manufacturer as per local requirements.

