# 9.7 Anticipated Clinical Benefits and Risks

#### 9.7.1 Known Potential Risks

Systane Complete Preservative-Free may cause mild eye burning or irritation, itching or redness of the eyes, watery eyes, blurred vision, or unpleasant taste in the mouth. There may be a rare possibility of an allergic reaction, which could be severe.

Systane Complete must be stopped in the event of eye pain, changes in vision, continued redness or irritation of the eye, or if condition worsens or persists for more than 72 hours.

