# 3.5. Analysis Visit Windows

As per the protocol, data will be collected for the assessments at the Screening/Baseline (Visit 1), 15-day Follow-up (Visit 2), and 30-day/Exit (Visit 3). The data will be collected within  $\pm 2$ 

days window for the Visit 2 and Visit 3. By-visit summaries will use the analysis visit. Scheduled, unscheduled and early termination visits will be windowed based on the following analysis visit window (Table 2).

- 1) If the scheduled records do not fall within a visit window, then the records will be flagged as out of the allowed window and the original visit from the eCRF will be assigned for the analysis visit. In case of unscheduled records not falling within a visit window, the original visit from the eCRF will be assigned.
- 2) For post-baseline visits, if there is more than 1 record available within the same visit window, the following rules will be applied:
  - a. Select the record collected at the scheduled visit.
  - b. If there are no records at the scheduled visit, then the record closest to the target day will be used.
  - c. If there are multiple records with the same distance to the target day, the latest record will be used.
- For Baseline visit, the last non-missing record among scheduled and unscheduled assessments will be selected.

Table 2: Analysis Visit Window

Analysis	Target Study	Visit Window for , IDEEL-SB, BCVA,	
Visit	Day	Biomicroscopy	
Baseline	1	<=1	
Visit 2	15	13 to 17	
Visit 3	30	28 to 32	

In general, only observations assigned to an analysis visit window will be included in the analysis. Data collected at unscheduled visits will be included in the data listings. In addition, any data collected out of the allowed window will be flagged in the listings.

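### Protocol 6.4.6 does not separate stopping the drops from leaving the study, so a subject who exits before Day 28 generally drops out of the Visit 3 BCVA and biomicroscopy-shift tables

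*Protocol*

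**What the plan says.** **Stopping the drops.** Protocol 9.7.1 states: "Systane Complete must be stopped in the event of eye pain, changes in vision, continued redness or irritation of the eye". The same rule covers a complaint that gets worse or lasts beyond 72 hours. SAP 6.3.1 foresees this, with a category for adverse events that lead to permanent discontinuation of the device.

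**Leaving the study.** Protocol 6.4.6 opens with "Participation of a subject in this clinical study may be discontinued for any of the following reasons" and lists adverse events, lack of efficacy and device problems among the reasons. On premature withdrawal, "study staff should make every effort to complete the full panel of assessments scheduled for the Early Exit Visit". Withdrawn subjects are not replaced. Protocol Table 4 marks IDEEL-SB, BCVA and biomicroscopy at the unscheduled or early-exit visit as done only where necessary.

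**Safety follow-up.** Protocol 9.2: "At each visit, after the subject has had the opportunity to spontaneously mention any problems, the Investigator should inquire about AEs". The same section makes any clinically relevant unfavourable change in a protocol parameter a reportable adverse event. Protocol 9.5 asks investigators for "any new safety information (which includes new AEs and changes to previously reported AEs" and follows events still open at exit until database lock.

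**Analysis.** SAP 3.5: "Scheduled, unscheduled and early termination visits will be windowed based on the following analysis visit window". SAP Table 2 sets Visit 2 at Days 13 to 17 and Visit 3 at Days 28 to 32, and SAP 3.5 generally restricts analysis to windowed observations. BCVA is summarised at Baseline and Visit 3 (SAP 6.3.2), and biomicroscopy shifts run from Baseline to Visit 3 (SAP 6.3.3). Change from Baseline needs a value at the visit in question (SAP 3.2), and missing values are not imputed (SAP 3.4).

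**The concern.** The reasons for stopping in 9.7.1 are largely what BCVA and slit-lamp examination measure: vision, redness and irritation. If stopping for one of these leads to exit, the subject loses the remaining scheduled adverse-event questioning and the Day 30 examination. The Early Exit examination, if done, generally does not enter the Visit 3 tables.

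BCVA and biomicroscopy are named safety endpoints, to be analysed in everyone who took at least one dose. Selective loss of the eyes that tolerated the drops badly would make those two Visit 3 summaries look somewhat better than the treated population. With no comparator, nothing else in the study would reveal it.

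**Working it through.** **1. The plan's own figure.** Protocol 6.4.1 gives a 95% half-width of 0.060 at n = 54 and p = 0.0543. Check: 1.96 × √(0.0543 × 0.9457 / 54) = 0.0604. It reproduces, and this point does not affect it.

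**2. Is there any instruction to keep the subject?** The nearest texts are:
- Protocol 6.4.6, missed visits: reschedule and counsel. This is triggered by a missed visit, not by stopping the drops.
- Protocol 7.6: a subject may continue after a deviation by agreement. This concerns deviations.
- Protocol 9.5: follow-up of adverse events. It schedules no examination.
- Inclusion criterion 5: willingness to use only the study device throughout. A subject who stops and resumes other tears no longer fits this, and no text says that the subject may remain.

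None of these asks for the Day 15 call and Visit 3 after stopping.

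**3. Where does an early exit land?** Exit days before the Visit 3 window are Days 2 to 27, so 27 − 2 + 1 = 26 days.

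| Exit day | Number of days | Analysis window (SAP Table 2) | Scheduled contacts missed |
|---|---|---|---|
| 2–12 | 11 | none | Day 15 call and Visit 3 |
| 13–17 | 5 | Visit 2 | Visit 3; the Day 15 call too if not yet made |
| 18–27 | 10 | none | Visit 3 |

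So 11 + 10 = 21 days are in no window, 5 are in Visit 2's, and none is in Visit 3's. Visit 2 has no planned BCVA summary and no shift table. Counting from a first dose on Day 1, the 72-hour rule can apply from about Day 4, before both remaining contacts. These are counts of days, not probabilities, because the documents give no distribution of exit times.

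**4. Size per subject.** Assume that all of the roughly 68 recruited subjects are treated: 68 × 2 = 136 eyes, and 2 / 136 = 1.5%. SAP 3.3 counts a subject as enrolled at consent, so fewer than 68 may be treated. If only 54 were, the share would be 2 / 108 = 1.9%.

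**5. Scale across the study.** No stopping rate is given. Two figures bound the discussion without estimating it.
- The planning proportion for any adverse event gives 0.0543 × 68 = 3.7 subjects, or about 7 of 136 eyes. Stops for adverse events would be only part of these. Nothing is given for lack of efficacy or device problems.
- The plan allows for 68 − 54 = 14 losses (14 / 68 = 20.6%). As an extreme, assume that all 14 are exits before Day 28 and that none of the 54 completers worsens. The Visit 3 summary then shows 0 of 54 (Clopper-Pearson upper limit 6.6%). If 1, 3 or 7 of the 14 had worsened, the rate over 68 would be 1.5%, 4.4% or 10.3%.

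**6. How firm is the mapping?** Not fully firm. SAP 3.5 names early termination visits but gives out-of-window rules only for scheduled and unscheduled records. SAP 3.1 permits, without requiring, unscheduled data in by-visit summaries. An early exit entered on the 30-day/exit form might keep a Visit 3 label. Hence the word generally.

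**The case against.** The strongest reply is that little of safety importance is lost. Four parts of it stand.

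- **Retention by default.** The wording of 6.4.6 is permissive, and no text ends participation because the drops stop. A subject who is not withdrawn remains on the visit schedule. A reader might infer that sites would let such subjects go unless told otherwise, but the documents do not show this. They show only that the matter is left to discretion.
- **Section 7.4.** It says: "In this study, there are no specific follow-up procedures or therapy transitions required". A reader might take this as releasing sites from following a subject who stops mid-study. The sentence after it concerns return to the usual care provider once the study is complete, so 7.4 does not bear on this point.
- **Adverse events are kept.** A reader might infer that the safety signal itself disappears. It does not. Clinically relevant worsening at Early Exit becomes an adverse event under 9.2 and is counted without a visit window. The ocular table has a row for events causing permanent discontinuation, and early-exit examinations are listed.
- **A Day 30 examination off the drops does not describe the device.** It may show recovery, and other tears may have been resumed. This limits what retention alone can achieve, so the finding at stopping must be tabulated as well.

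It is also argued that a descriptive single-arm study has no randomised comparison to protect. That is true, but the safety summaries are meant to describe everyone treated, and incomplete denominators still distort a description.

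**Conclusion.** The point holds as a minor one. The plan does not distinguish stopping the device from leaving the study and does not ask sites to keep a subject who stops. Under the SAP windows, a subject who exits on Days 2 to 27 is generally absent from the Visit 3 BCVA and biomicroscopy-shift summaries. The size is 2 of about 136 eyes (1.5%) per subject, assuming that all 68 are treated. The total is unknown because no stopping rate is stated.

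The conclusion rests on the usual reading of SAP 3.5, that an early-exit record outside the windows is not relabelled as Visit 3. It does not extend to the adverse-event tables, which are unaffected. The IDEEL-SB change at Visit 3 has the same gap. There, however, values obtained off the drops would not describe performance, so the remedy differs.

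**What to change.** **Protocol 6.4.6.** Add that a subject who permanently stops the device without withdrawing consent has the Early Exit panel at stopping and then stays for whichever of the Day 15 call and Visit 3 remain, for adverse events, BCVA and biomicroscopy. Record resumed tears as a concomitant medication change. Subjects who withdraw consent keep the current Early Exit procedure. The stopping rule in 9.7.1 is unchanged.

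**SAP 3.5, 6.3.2 and 6.3.3.** State which analysis visit an Early Exit record receives. Include off-treatment Visit 3 eyes in the full-analysis-set BCVA and shift tables, flagged. Add a row from Baseline to the last on-treatment examination, using Early Exit for subjects who stopped, so that the finding at stopping is also tabulated.

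**SAP 5.3.1.** Report off-treatment IDEEL-SB scores separately from the on-treatment performance summary.

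The flag needs a recorded stop date and reason. It should not rest on a last-dose date imputed under SAP 4.6. A disposition row for treatment discontinuation would be a small useful addition.

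**Cost.** A few sentences in each document, one eCRF field for treatment status with date and reason, and some extra table rows. The contacts are already scheduled. The downside is that a few Visit 3 values will come from subjects off the drops and must be read with their flag.

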#### 7 STUDY PROCEDURES

#### 7.1 Informed Consent

The Investigator or his/her representative will explain the nature of the study to the subject and answer all questions regarding the study.

Subjects must be informed that their participation is voluntary. Subjects will be required to sign a statement of informed consent that meets the requirements of 21 Code of Federal Regulations (CFR) 50, local regulations, International Conference on Harmonization (ICH) guidelines, Health Insurance Portability and Accountability Act (HIPAA) requirements, where applicable, and the IRB/IEC or study center.

The medical record must include a statement that written informed consent was obtained before the subject was enrolled in the study and the date the written consent was obtained. The authorized person obtaining the informed consent must also sign the ICF.

Subjects must be re-consented to the most current version of the ICF during their participation in the study.

A copy of the ICF must be provided to the subject.

# 7.2 Vulnerable Populations

Members of vulnerable populations will not be specifically targeted for recruitment. However, the intended subject population may include subjects who are considered to be vulnerable by definition. The procedures included in this protocol are sufficient to provide the necessary human subjects' welfare protections without the need for additional procedures.

#### 7.3 Clinical Procedures and Assessments

After obtaining informed consent, assessments will be conducted for the enrolled subject as described in the sections below. The Investigator is responsible for ensuring that responsibilities for all assessments are delegated to appropriately qualified site personnel.

# 7.3.1 Demographics

Age, sex, race, and ethnicity will be collected at the Screening/Baseline visit (D1).

#### 7.3.2 Medical History/Concomitant Medications

Fully document concomitant medications (taken within the past 30 days prior to the Screening/Baseline Visit) and Medical History (within 1 year prior to the Screening/Baseline

Visit) in the subject source documents (i.e., subject's chart). If the subject reports any condition in Table 3, the Investigator may ask for additional information at their discretion.

AEs are collected from the time of informed consent. Any preexisting medical conditions or signs/symptoms present in a subject prior to the start of the study (i.e., before informed consent is signed) are not considered AEs in the study and should be recorded in the Medical History section of the eCRF.

In the electronic data capture (EDC), only limited information regarding concomitant medications and medical history will be captured, as noted below.

- Medical History: Document all ocular history and targeted systemic history. In the EDC, there is a prepopulated dropdown field with items of interest that is consistent with Table 3.
- Concomitant medications: Document all ocular medications and targeted systemic medications used to treat conditions documented in Medical History and AEs.

**Table 3.** Targeted Medical History

Medical History	Definition	
Active Respiratory Infections	Principal respiratory viruses known to cause ocular disease in humans:  Adenovirus Influenza virus Respiratory syncytial virus Coronavirus Rhinovirus Human metapneumovirus	
Alcohol Abuse	Heavy drinking: current or past consumption of 4 or more servings of alcoholic beverages daily	
Atopic Disease	
 
Atopy
 
Atopic dermatitis
 
Urticaria
 
Angioedema
 
Asthma
 
Allergic rhinitis
 
	
Cancer	
 
Cancers (potentially metastatic to eye or orbit), e.g., breast and lung cancer for women, gastrointestinal cancer for men, etc.
 
Cancers on active chemo- or radiotherapy
 
	
Diabetes Mellitus	All Type I and II, some potential risk factors for retinopathy include:	
Headache	Confirmed diagnosis (regardless of frequency of attacks) of:	

Medical History	Definition
·	
 
Tension-type headache
 
Cluster headache
 
Headache with symptoms:
 
Systemic symptoms (e.g., fever, weight loss)
 
Neurologic symptoms/signs
 

	
 
Onset (sudden)
 
Older age (over 50 years)
 
Prior history (new headache)
 
Secondary illnesses (HIV or history of neoplasia)
 

Hypertension	

Chronic long-standing hypertension

Acute severe hypertension

HIV Infection	
 
Human immunodeficiency virus (HIV) disease with or without highly active antiretroviral therapy (HAART)
 
Low CD+ T-cell count (<100 cells /μL) is associated with severe ocular manifestations
 

Lupus	Systemic Lupus Erythematosus (SLE) is a chronic, idiopathic, multisystem inflammatory disease characterized by hyperactivity of the immune system and prominent autoantibody production
Multiple Sclerosis	Multiple sclerosis (MS) is a chronic relapsing and remitting, episodic demyelinating disease of the central nervous system
Rheumatoid Arthritis	Rheumatoid Arthritis (RA) is a chronic inflammatory autoimmune disease of unknown etiology that affects approximately 1% of the global population
Rosacea	
 
Rosacea with any subtype below:
 
Erythemato-telangiectatic
 
Papulopustular
 
Phymatous
 
Ocular rosacea
 

Sarcoidosis	Sarcoidosis is a systemic inflammatory disease of unknown etiology characterized by the formation of noncaseating granulomas.
Scleroderma	Systemic sclerosis sine scleroderma is a rare, chronic autoimmune disease with unknown etiology. Its prominent features are fibrosis, vasculopathy, and impaired immune response.
Seronegative spondyloarthropathies	
 
Ankylosing spondylitis
 
Reactive arthritis
 
Bechet's disease
 
Inflammatory bowel diseases
 
Psoriatic arthritis
 

Sjogren's Syndrome	

Primary Sjogren's syndrome

Secondary Sjogren's syndrome

Smoking	
 
Current smoker (regardless of number of pack-years)
 
Former smoker (cessation < 20 years before the study)
 

Systemic Herpes Zoster Infection	A viral infection caused by varicella-zoster characterized by painful rash with blisters.
Thyroid Disorder	
 
Hyperthyroidism (e.g., Graves' disease)
 
Hypothyroidism (e.g., Hashimoto's thyroiditis)
 
Euthyroid
 

<ocular other="" –=""></ocular>	[Specify - if not indicated above]

# 7.3.3 Efficacy Assessments

Planned time points for all efficacy assessments are provided in Table 4.

#### 7.3.3.1 IDEEL-SB

Dry eye symptoms will be assessed using the IDEEL-SB questionnaire (see Appendix 17.2.1) at the Screening/Baseline visit (D1), before Systane Complete PF use, and at Visit 3 (and at unscheduled and at early exit visits, as necessary).

The IDEEL-SB (Version 1) symptom bother module consists of 20 questions that assess general dry eye symptoms a subject experiences. It should be administered prior to performing any other study testing procedure. The subject's response to each question will be entered on paper and scored to determine the eligibility of the subject to participate in the study.

#### **Administration and Scoring**

A paper copy of the IDEEL-SB module will be given to each subject for completion without assistance. All questions should be answered by the subject so please check the questionnaire before the subject leaves the study visit.

Question 1 is scored on a 5-point Likert-type scale where 0 = None of the time, 1 = A little of the time, 2 = some of the time, 3 = Most of the time, and 4 = All of the time. Questions 2-20 are scored on a 4-point Likert-type scale where 0 = I did not have this symptom / Not Applicable, 1 = Not at all, 2 = Slightly, 3 = Moderately, 4 = Very much.

The subject will be instructed to select a single response that best represents their answer. The score is calculated if at least 50% (10 items) of the 20 items within the dimension are completed; non-missing; otherwise the score is set to missing. The Symptom Bother score is calculated as the mean value of the non-missing item scores 1-20 multiplied by 25.

Sum of responses from questions 1- 20  $\times$  25 = IDEEL SB score Number of questions (1-20) answered

The final calculated IDEEL-SB score for each patient will be entered into the study source documents to determine eligibility at the Screening Visit.

